PROTOCOL

A phase II clinical trial of DARC

A Phase II, Open label, single centre, non-randomised phase II trial to further investigate DARC technology using ANX776 in healthy subjects and patients diagnosed with Glaucoma, Age-related Macular Degeneration, Down's Syndrome and Optic Neuritis

Protocol Version	V3.0
Date	10 th November 2016
Sponsor	University College London
Sponsor Ref #	15/0959
Comprehensive Clinical Trials Unit Trial Adoption Group #	CCTU/'2015/240
Trial registration	ISRCTN: 10751859
CTA #	31894
NRES #	16/LO/1700
Public title	A Phase II Clinical Trial of DARC (DARC II)
Countries of Recruitment	UK
Health Condition(s) or Problem(s) Studied	Glaucoma, AMD, Optic Neuritis, Down's Syndrome
Intervention	Intravenous injection of a single dose of ANX776 (0.4mg) followed by assessment of retinal cells apoptosis performed using diagnostic retinal imaging
Study Type	Open label, single centre, non-randomised phase II trial to further investigate DARC technology using ANX776 in healthy subjects and patients diagnosed with Glaucoma, Age-related Macular Degeneration, Down's Syndrome and Optic Neuritis
Date of First Enrolment	1st January 2017
Target Sample Size	120 participants: 
- Healthy volunteers: 40 subjects- Glaucoma: 20 subjects- AMD: 20 subjects- Down's syndrome: 20 subjects- Optic Neuritis: 20 subjects

Table of Contents

1. Trial design	4
2. Trial Diagram	4
3. Abbreviations	5
4. Methods	6
4.1. Site Selection	6
4.1.1. Study Setting	6
4.1.2. 6.1.2 Site/Investigator Eligibility Criteria	6
4.1.3. Principal Investigator's (PI) Qualifications and Agreements	6
4.1.4. Resourcing at Site	6
4.2. Site approval and activation	6
5. Participants	7
5.1. Eligibility Criteria	7
5.1.1. Participant selection	7
5.2. Inclusion Criteria	7
5.2.1. General Participant Inclusion Criteria	7
5.2.2. Group Specific Participant Inclusion Criteria	7
5.2.3. Exclusion Criteria	8
5.3. Eligibility Criteria for Individuals Performing the Interventions	9
5.4. Co-enrolment Guidance	9
5.5. Screening Procedures	10
5.6. Informed Consent Procedure	10
5.6.1. Informed Consent for Optic Neuritis, AMD & Glaucoma Patients	10
5.6.2. Informed Consent for Down's Syndrome Participants	10
5.6.3. Informed Consent for Healthy Volunteers	12
5.6.4. Informed Consent for Optional Exploratory fNIRS	12
6. Interventions	12
6.1. Description of intervention	12
6.2. Treatment Schedule	12
6.3. Dispensing	12
6.4. Accountability	12
6.5. Source of IMPs including placebo	13
6.6. Compliance and Adherence	14
6.7. Concomitant Care	14
6.8. Overdose of Trial Medication	14
6.9. Protocol Treatment Discontinuation	14

6.10.	Accountability procedures for investigational products	14
6.11.	Contingency planning for abnormal findings	15
7.	Outcomes	15
7.1.	Primary Outcomes	15
7.2.	Secondary Outcomes	15
8.	Participant Timeline	15
9.	Procedures	16
9.1.	Qualification/ pre-intervention assessment	16
9.2.	Treatment procedures	17
9.3.	Intervention (within 12 weeks of Qualification)	17
9.4.	Safety follow up telephone call (30 days after intervention)	17
9.5.	Early Stopping of Follow-up	17
9.6.	Loss to Follow-up	17
9.7.	Trial Closure	17
9.8.	Data queries	18
10.	Ethics and Dissemination	18
10.1.	Research Ethics Approval	18
10.2.	Competent Authority Approvals	18
10.3.	Other Approvals	18
10.4.	Protocol Amendments	19
10.5.	Consent or Assent	19
10.6.	Confidentiality	19
10.7.	Declaration of Interests	20
10.8.	Indemnity	20
10.9.	Finance	20
10.10.	Archiving	20
10.11.	Access to Data	20
10.12.	Ancillary and Post-trial Care	20
10.13.	Publication Policy	21
10.13.1.	Trial Results	21
10.13.2.	Authorship	21
10.13.3.	Reproducible Research	21

1. Trial design

This Phase II trial will be a single-centre, open-label, cross-sectional study in patients diagnosed with Glaucoma, Age-related Macular Degeneration, Optic Neuritis, individuals with Down's syndrome, and healthy volunteers.

A sample size of 120 subjects is planned in 5 study groups:

[figure not shown]
- Healthy volunteers: 40 subjects
- Glaucoma: 20 subjects
- Age-related Macular Degeneration: 20 subjects
- Optic Neuritis: 20 subjects
- Down's Syndrome: 20 subjects

The Down's syndrome participants will be recruited and receive the intervention last.

Subjects in each study group will receive the same amount of ANX776 and each individual subject will receive 1 single intravenous injection. All subjects will be enrolled in accordance with the inclusion and exclusion criteria outlined in Section xxx and via the recruitment strategy in Section xxx.

DARC imaging will be performed in all participants to assess retinal cell apoptosis. However, in a subset of participants (as described in section xxx), fNIR spectroscopy will be performed simultaneously as an optional procedure.

2. Trial Diagram

3. Abbreviations

AE	Adverse Event
Anx-A5	Annexin A5
AR	Adverse Reaction
AMD	Age-related Macular Degeneration
CI	Chief Investigator
CRF	Case Report Form
cSLO	Confocal Scanning Laser Ophthalmoscope
CTA	Clinical Trial Authorisation
CCTU	Comprehensive Clinical Trials Unit
DARC	Detection of Apoptosing Retinal Cells
DSUR	Development Safety Update Report
EU	European Union
FDA	(US) Food and Drug Administration
fNIRS	Functional Near-Infrared Spectroscopy
FWA	Federal Wide Assurance
GCP	Good Clinical Practice
GS	Glaucoma Suspect
ICF	Informed Consent Form
ICH	International Conference on Harmonisation
IDMC	Independent Data Monitoring Committee
IMP	Investigational Medicinal Product
IOP	Intraocular pressure
IRB	Institutional Review Board
ITT	Intention to Treat
MHRA	Medicines and Healthcare products Regulatory Agency
MS	Multiple Sclerosis
NIRS	Near-Infrared Spectroscopy
OCT	Optical Coherence Tomography
OHT	Ocular Hypertension
PED	Pigment Epithelial Detachment
PI	Principal Investigator
PIN	Participant Identification Number
PIS	Participant Information Sheet
PS	Phosphatidylserine
QA	Quality Assurance
QC	Quality Control
QMMP	Quality Management and

	Monitoring Plan
R&D	Research and Development
REC	Research Ethics Committee
RGC	Retinal Ganglion Cell
RNFL	Retinal Nerve Fibre Layer
RPE	Retinal Pigmented Epithelium
RRMS	Relapsing-Remitting Multiple Sclerosis
SAE	Serious Adverse Event
SAP	Statistical Analysis Plan
SAR	Serious Adverse Reaction
SPC	Summary of Product Characteristics
SPMS	Secondary Progressive Multiple Sclerosis
SSA	Site Specific Approval
SUSAR	Suspected Unexpected Serious Adverse Reaction
TMF	Trial Master File
TMG	Trial Management Group
TMT	Trial Management Team
ToR	Terms of Reference
TSC	Trial Steering Committee
UCL	University College London

4. Methods

4.1. Site Selection

The trial sponsor has overall responsibility for site and investigator selection and has delegated this role to CCTU.

4.1.1. Study Setting

The Trial will be conducted at 1 site in the UK, all patients will be recruited from the NHS clinics at the Western Eye Hospital, Imperial College Healthcare NHS Trust. Down's Dydrome (DS) participants will be identified by the research team at Intellectual and Developmental Disabilities Research Group (CIDDRG) from the cohorts of people with DS who have previously consented to be contacted about future studies.

4.1.2. 6.1.2 Site/Investigator Eligibility Criteria

Once the site has been assessed as being suitable to participate in the trial, the trial team will provide them with a copy of this protocol and relevant Summary of Product Characteristics (SPC) or Investigator Brochures (where appropriate).

To participate in the DARC II trial, investigators and trial sites must fulfil a set of criteria that have been agreed by the DARC II Trial Management Group (TMG) and that are defined below.

Eligibility criteria:

- A named clinician is willing and appropriate to take Principal Investigator responsibility
- Suitably trained staff are available to recruit participants, enter data and collect samples
- For IMP trials the site should have a pharmacy that is able to store, prepare and dispense IMP appropriately

4.1.3. Principal Investigator's (PI) Qualifications and Agreements

The investigator(s) must be willing to sign a CCTU Clinical Trial Agreement or an Investigator Agreement to comply with the trial protocol (confirming their specific roles and responsibilities relating to the trial, and that their site is willing and able to comply with the requirements of the trial). This includes confirmation of appropriate qualifications, familiarity with the appropriate use of any investigational products, agreement to comply with the principles of GCP, to permit monitoring and audit as necessary at the site, and to maintain documented evidence of all staff at the site who have been delegated significant trial related duties.

4.1.4. Resourcing at Site

The investigator(s) should be able to demonstrate a potential for recruiting the required number of suitable subjects within the agreed recruitment period (i.e. the investigator(s) regularly treat(s) the target population). They should also have an adequate number of qualified staff and facilities available for the foreseen duration of the trial to enable them to conduct the trial properly and safely.

Sites will be expected to complete a delegation of responsibilities log and provide staff contact details.

The site should have sufficient data management resources to allow prompt data return to CCTU.

4.2. Site approval and activation

The Clinical Trial Authorisation (CTA) for the trial requires that the Medicines and Healthcare products Regulatory Agency (MHRA) is supplied with the names and addresses of all participating sites and named Principal Investigators. Trial staff at CCTU will perform this task.

On receipt of the signed Clinical Trial Agreement or Investigator Agreement, approved delegation of responsibilities log and staff contact details, written confirmation will be sent to the site PI. The CCTU will notify the PI in writing of the plans for site initiation. Sites will not be permitted to recruit any patients until a letter for activation has been issued. The Trial Manager or delegate will be responsible for issuing this after a green light to recruit process has been completed.

The site must conduct the trial in compliance with the protocol as agreed by the Sponsor and, by the regulatory authority(ies) (as appropriate), and which was given favourable opinion by the Research Ethics Committee (REC) and/or Institutional Review Board (IRB). The PI or delegate must document and explain any deviation from the approved protocol, and communicate this to the trial team at CCTU.

5. Participants

5.1. Eligibility Criteria

5.1.1. Participant selection

There will be **NO EXCEPTIONS** (waivers) to eligibility requirements for the DARC II trial. Questions about eligibility criteria should be addressed PRIOR to attempting to enrol a participant.

The eligibility criteria for this trial have been carefully considered and are the standards used to ensure that only medically appropriate participants are entered. Participants not meeting the criteria should not be entered into the trial for their safety and to ensure that the trial results can be appropriately used to make future treatment decisions for other people with similar diseases or conditions. It is therefore vital that exceptions are not made to these eligibility criteria.

Participants will be considered eligible for enrolment in this trial if they fulfil all of the **general** inclusion criteria and none of the **general** exclusion criteria as defined below.

Patients should then be assessed against the inclusion and exclusion criteria of the specific study group that they are being enrolled into the trial for.

Eligibility criteria should be confirmed by 2 clinicians ensuring the PI signs to confirm eligibility before the patient is enrolled. Prior to enrolment subject eligibility status will be confirmed against eligibility criteria by study investigators and signed off by one of the Principal Investigators.

5.2. Inclusion Criteria

5.2.1. General Participant Inclusion Criteria

- Age \geq 18 years.
- Clear optical media in the studied eye.
- Refractive error not higher than spherical equivalent of 10 D and best corrected visual acuity equal to 6/24 or better at qualification.
- Women of childbearing potential identified as not pregnant and have consented to complete a pregnancy test.
- Subjects who have capacity to consent, have personally signed and dated the informed consent document indicating that they have been informed of all pertinent aspects of the study.

5.2.2. Group Specific Participant Inclusion Criteria

- No table of contents entries found. Glaucoma group subjects will show progression in one or more of the parameters measured and will have at least one eye with a diagnosis of glaucoma (abnormal optic disc and/or visual field defect or both); be diagnosed as a glaucoma suspect or ocular hypertensive (elevated IOP).

- Subjects proven to be able to perform reliable visual field testing using the HFA 640, central 24-2 program, to yield full thresholds, and have had good funduscopy with assessment of their optic disc.

5.2.2.1. Down's Syndrome Participant Inclusion Criteria

- Down's Syndrome.

5.2.2.2. AMD Participant Inclusion Criteria

- Patients with AMD as defined by:
 - Early AMD mainly characterised by drusen, retinal pigment epithelium (RPE) pigment changes.
 - Late AMD mainly characterised as: geographic atrophy of the RPE (dry AMD).
- Neovascular AMD (wet AMD).

5.2.2.3. Optic Neuritis Participant Inclusion Criteria

- Clinical diagnosis of optic neuritis affecting one eye within two years.
- Visual acuity in affected eye \leq 6/12 at worst point.
- Corrected vision in unaffected eye \geq 6/6.
- No history of optic neuritis or other ocular disease in either eye prior to the episode of optic neuritis.
- Subjects proven to be able to perform reliable visual field testing using the HFA 640, central 24-2 program, to yield full thresholds, and have had good funduscopy with assessment of their optic disc.

5.2.2.4. Healthy Volunteers Participant Inclusion Criteria

- Confirmation of medical history as confirmed by General Practitioner.
- No evidence of any eye disease.

5.2.2.5. Exploratory Optional fNIRS Inclusion Criteria

- Participants who are bald, or with short (less than 3cm), fair (unpigmented) hair

5.2.3. Exclusion Criteria

5.2.3.1. General Participant Exclusion Criteria

- Presence of severe, unstable or uncontrolled systemic disease.
- Known intolerance to IMP.
- Body weight <40kg or >150kg.
- Inability to comply with the study or follow-up procedures.
- Any subjects with a known history of clotting diseases (including DVTs), and subjects taking anticoagulants.
- Ocular surgery within the past 3 months or planned surgery in the study eye, during the course of the trial.
- Pregnant or lactating, or not using adequate contraception* for the duration of the trial (and 30 days post injection of study drug).
- Currently being treated for cancer or any other disease likely to adversely affect participation in this study.
- AIDS / HIV.
- History of alcoholism or drug addiction.
- History or active uveitis.
- History of systemic vasculitis, collagenosis or ongoing treatment of cancer.
- Evidence of previous retinal vascular disease.

- Individuals with terminal illness, or mental illness affecting their compliance with the study
 - Any other disease, condition or laboratory abnormality that in the opinion of the CI may increase the risk for the participation or may interfere with the interpretation of study results and in the judgement of the Investigator would make the subject inappropriate for entry into the study.
 - Central corneal thickness <450 pm or >650pm.
 - Currently, or within the last 3 months, enrolled in a clinical trial of an investigational medicinal product.
 - History of retinal laser photocoagulation.
 - Media opacities or retinal pathology or amblyopia significantly limiting visual acuity, visual field test or retinal imaging.
 - Any other condition or pathological process that in the opinion of the investigator would not make the patient suitable for the trial.
- * For the purposes of this study, females will be considered of childbearing potential unless they are naturally postmenopausal or permanently sterilised (i.e. hysterectomy). For women of childbearing potential who may participate in the study, the following reliable form of contraception are acceptable (e.g. oral contraceptive and condom, intra--uterine device (IUD) and condom, diaphragm with spermicide and condom).

5.2.3.2. Group Specific Participant Exclusion Criteria

5.2.3.3. Glaucoma Participant Exclusion Criteria

- Uncontrolled IOP >24mmHg.
- Angle closure/narrow glaucoma. Mean deviation at HVF >12dB.

5.2.3.4. Down's Syndrome Participant Exclusion Criteria

- Lack of capacity to consent.
- Significant learning disability
- Dementia

5.2.3.5. AMD Participant Exclusion Criteria

- Presence of ocular conditions with increased risk of choroidal neovascularisation (CNVM).
- Current or past use for more than 30 days of chloroquine, hydroxychloroquine, chlorpromazine, thioridazine, quinine sulfate, clofazimine, cisplatin, carmustine, (BCNU), deferoxamine, amiodarone, isotretinoin, or gold.

5.2.3.6. Optic Neuritis Participant Exclusion Criteria

- Corticosteroid use in the past 2 months.

5.2.3.7. Healthy Volunteers Participant Exclusion Criteria

- Evidence of any historical retinal eye disease.

5.2.3.8. Exploratory Optional fNIRS Exclusion Criteria

- There are no specific exclusion criteria for the exploratory optional fNIRS.

5.3. Eligibility Criteria for Individuals Performing the Interventions

The IMP should be administered by a study investigator in adherence with the trial administration SOP and also the hospital's policies and procedures for intravenous injections.

5.4. Co-enrolment Guidance

The Principal investigator or Co-Investigator(s) at trial sites will be responsible for ascertaining whether the patient is currently taking part in any clinical trial. All patients will only be enrolled once into the DARC II trial. The investigator will be responsible for checking the patient notes against the screening/enrolment log at site prior to screening to ensure that the patient is not already enrolled in the trial.

Patients may not be enrolled if currently taking part in any other trial of an IMP without the permission of the Chief Investigator. Co-enrolment in observational studies is acceptable.

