7.2. Secondary Outcomes

Safety is defined as absence of an adverse event of grade 3 or above in the following study groups:

- 20 participants with AMD,
- 20 participants presenting with acute vision loss from optic neuritis,
- 20 participants with Down’s syndrome,
- 20 participants with glaucoma,
- 40 healthy volunteers.

Safety will be measured by adverse events following the Common Terminology Criteria for Adverse Events (CTCAE) scale.

In addition, in a subset of participants, an exploratory secondary objective is to assess if the ANX776 signal is detected in the brain using fNIR spectroscopy.

8. Participant Timeline

Figure 1: Participant Timeline

Type of procedure	Procedure	Study Visit
Qualification Procedures	Informed Consent	X
	Medical and Ophthalmic Histories	X
	Prior & Concomitant Medications/Procedures	X
	Demographic data	X
	Cognitive Ability Assessments	X ⁸
	Dementia Diagnosis Interview	X ⁹
	Physical Examination	X
	Vital Signs	X

	Visual Acuity	X⁴
	Slit-Lamp Bio-microscopy (incl. Corneal Pachymetry and IOP)	X⁴
	Visual Field (HVF)	X, X, X^{1,3,4}
	Fundus Exam (Post-Pupil Dilation)	X⁴
	Baseline fundus autofluorescence (IR)*	X⁴
	Optical Coherence Tomography (OCT)	X, X, X^{1,3,5}
	Heidelberg Retinal Tomography (HRT)	X, X, X^{1,3,4}
	Childbearing potential / pregnancy test	X
	Eligibility Confirmed	X
Intervention Procedures	Intravenous Administration of Study Drug - ANX776	X⁶
	DARC assessment by cSLO Retinal Imaging*	X, X, X, X^{2,6}
	Adverse Medical Event Query	X⁶
Post intervention	Safety follow up telephone call	X⁷

1. Up to 2 reliable historical tests, obtained no more than 24 months prior to the qualification / pre-intervention visit, can be used as part of this qualification assessment of Glaucoma, healthy volunteers, AMD, Downs syndrome and Optic Neuritis subjects.
 2. During injection, 15 min, 2 hours and 4 hours post injection.
 3. Confirmation of historical findings for Glaucoma, Optic neuritis and AMD participants.
 4. Down's participants are exempted from this test.
 5. For Down's participants, historical data will be used.
 6. Can be conducted up to 12 weeks from confirmation of eligibility.
 7. 30 days after DARC Intervention +/- 1 week
 8. Down's participants only
 9. Down's participants' parent /carer only
- * In a subset of participants this will be done in conjunction with fNIR spectroscopy (as described in section xxx)

9. Procedures

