9.1. Qualification/ pre-intervention assessment

Procedures performed before the intervention:

- Serious and Adverse Medical Event Query, Medical and Ophthalmic Histories, Prior and concomitant Medication/Procedures will be documented.
- Inclusion/Exclusion criteria will be evaluated.
- Demographic data, Ocular History, Physical Examination, Vital Signs, Visual Acuity, Slit-Lamp Bio-microscopy, Corneal Pachymetry, Intraocular Pressure, Visual Field, Fundus Exam (Post-Pupil Dilation), Cup/Disc Ratio (Post-Pupil Dilation), , Baseline fundus autofluorescence (488 and IR) will be performed.
- Glaucoma and healthy volunteers will require a minimum of 3 Visual field tests, 3 OCT and 3 HRT's to assess baseline characteristics. However, up to 2 reliable historical tests, obtained no more than 9 months prior to qualification, can be used for these tests in the Glaucoma group.
- AMD and Optic Neuritis subjects will have an OCT assessment confirming the status of the disease.

- For Down’s syndrome participants, due to their characteristics, historical data will be used.

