10.7. Declaration of Interests

The Chief Investigator for this trial is a named Inventor on the granted DARC patent which is owned by UCLB, and is unlicensed. We have therefore aimed to mitigate any risks arising from conflict of interest by using Principal Investigators for each affected group. The Chief investigator will not personally be involved in the recruitment, IMP administration nor follow up assessment for all trial patients. Data resulting from the trial will be monitored by an Independent Data Monitoring Committee.

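### Section 5.4 lets the Chief Investigator permit current co-enrolment that Sections 5.1.1 and 5.2.3.1 forbid, and no stated step re-applies time-dependent exclusions before an injection up to 12 weeks after sign-off

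*Protocol*

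**What the plan says.** **Co-enrolment.** Section 5.1.1 rules out waivers and closes with "It is therefore vital that exceptions are not made to these eligibility criteria". The general exclusions in Section 5.2.3.1 include "Currently, or within the last 3 months, enrolled in a clinical trial of an investigational medicinal product", with no provision for permission. Section 5.4 then states "Patients may not be enrolled if currently taking part in any other trial of an IMP without the permission of the Chief Investigator". On the Chief Investigator, who is a named inventor on the DARC patent, Section 10.7 says: "The Chief investigator will not personally be involved in the recruitment, IMP administration nor follow up assessment for all trial patients".

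**Timing.** Section 9.1, the qualification assessment, contains the line "Inclusion/Exclusion criteria will be evaluated". Section 9.2 places enrolment after qualification. Footnote 6 to Figure 1 (Section 8) says of the injection, the DARC imaging and the adverse event query: "Can be conducted up to 12 weeks from confirmation of eligibility". The heading of Section 9.3 gives the same 12 weeks. Figure 1 shows one pregnancy test, among the qualification procedures.

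Several exclusions depend on the date at which they are judged. In Section 5.2.3.1 these are pregnancy, other-trial enrolment and ocular surgery within 3 months. Section 5.2.3.6 adds, for the optic neuritis group, "Corticosteroid use in the past 2 months".

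**The concern.** A site with a candidate who is now in another IMP trial finds one section that forbids enrolment and another that opens it on request. Two investigators could read the same protocol and act differently, each with a section in support. The discretion is given to the one person whom Section 10.7 sets apart from recruitment because of a declared interest.

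The timing question is different in kind. A criterion met at qualification may no longer be met when ANX776 is given. A participant could become pregnant, join another trial, start a corticosteroid or have unplanned eye surgery in between. The protocol does not say that anyone must apply the exclusions again before the injection.

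Both matter because safety is a stated outcome in small groups (Section 7.2), and because safety data from as few as 20 participants inform whether Down's syndrome recruitment may begin (Section 5.6.2). A second investigational product would make a serious event harder to attribute. A pregnancy unknown at injection would breach the protocol's own exclusion.

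**Working it through.** The protocol gives no figure to reproduce here. The check is a comparison of sections, with simple arithmetic on time and group size.

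**1. Co-enrolment rules side by side**

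| Case | 5.1.1 and 5.2.3.1 | 5.4 |
|---|---|---|
| Now in another IMP trial, no permission | Excluded | Not enrolled |
| Now in another IMP trial, Chief Investigator permits | Excluded, no exceptions | May be enrolled |
| Left another IMP trial within 3 months | Excluded | No IMP-trial rule stated |

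Only the second row conflicts. No other exclusion carries a permission clause.

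**2. Interval from sign-off to injection**

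Maximum interval = 12 weeks × 7 = 84 days. If the single scheduled pregnancy test is done on the day eligibility is confirmed, it can be up to 84 days old at injection.

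**3. What is looked at on the injection day**

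| Time-dependent exclusion | Listed in Section 9.3? |
|---|---|
| Pregnancy | No test listed |
| Enrolment in another IMP trial | No check listed |
| Corticosteroids (optic neuritis only) | Concomitant medication is documented; no consequence stated |
| Recent ocular surgery | Procedures are documented and the eye is examined; no consequence stated |

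Section 5.4 makes the investigator responsible for finding out about other trials, but does not tie that to the injection day. Section 9.3 has no counterpart to the line in Section 9.1 on evaluating the criteria.

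**4. Sensitivity of the safety outcome**

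One event of grade 3 or above changes a group's proportion by 1/20 = 5 percentage points, or by 1/40 = 2.5 points in the healthy volunteers. This shows what one misattributed event would do. It does not estimate how often that would happen.

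**The case against.** **On co-enrolment.** Section 10.7 bars personal involvement in recruitment, not every opinion on eligibility, and Section 5.2.3.1 itself gives the Chief Investigator a judgement on participant risk. That stands: the tension with Section 10.7 is awkward, not a plain contradiction. A reader might also infer that the Chief Investigator has a financial hold on the product. The section says only that this person is a named inventor on an unlicensed patent owned by UCLB. None of this removes the conflict between Sections 5.1.1, 5.2.3.1 and 5.4.

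**On timing.** This objection is stronger, and much of it stands.
- Section 5.2.3.1 looks forward as well as back. It excludes planned surgery in the study eye during the trial, and it requires adequate contraception throughout and for 30 days after injection. Contraceptive failure and unplanned surgery remain possible, but the gap is narrower than the look-back windows alone suggest.
- Section 9.3 repeats physical examination, visual acuity, slit-lamp, intraocular pressure and fundus examinations, and cognitive and dementia assessments in Down's syndrome. It also records adverse events and concomitant medication. Section 6.9 allows treatment to be stopped after a change in condition. What is missing is an instruction to re-apply the criteria, not re-assessment as such.
- The procedure lists are incomplete. Section 9.1 omits the pregnancy test that Figure 1 shows, and the intervention rows of Figure 1 omit examinations that Section 9.3 lists. Section 5.3 refers to an administration SOP that is not shown. Silence in one list is therefore weaker evidence than a stated rule would be.
- Twelve weeks is a maximum, and Section 9.6 describes a single-visit trial.

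A reader might set the 84 days against the 2-month corticosteroid window and take the difference as the size of the problem. It is not. A course begun the day after sign-off defeats the exclusion whatever the length of the look-back, and the rule covers only the optic neuritis group, 20 of 120 participants.

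**Conclusion.** The co-enrolment contradiction is certain, because it can be read directly from three sections. Its scope is one half of one exclusion: current enrolment in another IMP trial.

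The timing gap is real but smaller. The protocol as shown has no stated step that re-applies the time-dependent exclusions before injection, and its only scheduled pregnancy test may be 84 days old by then. This part assumes that no such step sits in the administration SOP.

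Three stronger readings are not supported:
- **That eligibility exclusions in general can be waived.** Only Section 5.4 contains a permission, and it reaches no other criterion.
- **That ineligible participants would be dosed and then counted in the analysis.** The rule in Section 9.5 on keeping data concerns people who withdraw after the intervention. How an ineligible dosed participant is handled may be set in the statistical analysis plan, which is not shown.
- **That the DARC count would be distorted.** The protocol does not say that corticosteroids, surgery or another IMP alters it.

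The protocol gives no breach rate, so neither the number of participants affected nor any effect on the results can be quantified. The reason to act is that the text gives sites conflicting instructions on who may be dosed, and the repair is small.

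**What to change.** 1. Reconcile Sections 5.1.1, 5.2.3.1, 5.4 and 10.7 so that one rule on co-enrolment stands. Deleting the permission clause in Section 5.4 would follow the protocol's own no-waiver rule. If the sponsor wants to keep the discretion, Sections 5.1.1 and 5.2.3.1 must say so openly, and Section 10.7 must be squared with it.
2. Reconcile Section 5.2.3, Figure 1 and Section 9.3. Add a separate line to Section 9.3 that the time-dependent eligibility criteria, including pregnancy status, are re-confirmed before injection, and show it in Figure 1. How each is confirmed is for the sponsor to decide.
3. Leave the existing eligibility sign-off and the 12-week window as they are. Moving the sign-off to the injection day would clash with Sections 5.1.1 and 9.2, which place it before enrolment, and would empty footnote 6 of meaning.

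The cost is a short checklist on the injection day, an occasional late screen failure and a protocol amendment. Section 10.4 gives eligibility changes as an example of a substantial amendment and requires such amendments to have ethical approval before use, so this is more than an editorial correction.
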